## 6 CLINICAL AND LABORATORY EVALUATIONS/STUDY PROCEDURES

### 6.1 Schedule of Activities - Table 7

Evaluation	Screening (Month -4, v1)	Month  -2 (v2)	Random- ization/ Baseline (Month 0, v3)	Months (visit #) 											Follow up (Month 17, v15) 
				1 (v4) 20	2 (v5)	3 (v6) 20	4 (v7)	6 (v8)	8 (v9)	9 (v10) 20	10 (v11)	12 (v12)	14 (v13)	16  (v14)	
Written Informed Consent	X														
Inclusion/Exclusion Review	X	X	X	X	X	X	X	X	X	X	X	X	X	X	X
Documentation of Disease/Disorder	X														
Medical History/Demographics	X														
Autism Diagnostic Observation Scale 		X 													
Vital Signs: HR, BP (sitting)	X	X	X	X	X	X	X	X	X	X	X	X	X	X	X
Weight	X	X	X	X	X	X	X	X	X	X	X	X	X	X	X
Height	X	X	X	X	X	X	X	X	X	X	X	X	X	X	X
Physical & Psychiatric Examination	X	X	X	X	X	X	X	X	X	X	X	X	X	X	X
Neurological Examination	X	X	X	X	X	X	X	X	X	X	X	X	X	X	X
Funduscopic Examination 	X	X	X		X		X		X		X	X		X	X
EKG	X 				X				X		X			X	
Concomitant Medication/Therapy Review	X	X	X	X	X	X	X	X	X	X	X	X	X	X	X
Safety Labs 	X 				X				X		X			X	
Research Labs for Biomarkers 	X 				X				X		X			X	
Blood PK Sampling	X 				X				X		X			X	
Urine dipstick	X 				X				X		X			X	
Randomization 				X											

AFQ056 for Language Learning in Children with FXS

Version v15

Version date 02/03/2021

Evaluation	Screening (Month -4, v1)	Month  -2 (v2)	Random- ization/ Baseline (Month 0, v3)	Months (visit #) 											Follow up (Month 17, v15) 17
				1 (v4) 20	2 (v5)	3 (v6) 20	4 (v7)	6 (v8)	8 (v9)	9 (v10) 20	10 (v11)	12 (v12)	14 (v13)	16  17 (v14)	
Dispense Study Drug	X	X	X		X		X	X	X		X	X	X	X	
Dose Review/Titration 			X	X					X	X					X 
Drug Accountability/Compliance 		X	X		X		X	X	X		X	X	X	X	X
Adverse Event Review		X	X	X	X	X	X	X	X	X	X	X	X	X	X
Suicidality Screen	X	X	X	X	X	X	X	X	X	X	X	X	X	X	X
Implement/Review Language Intervention/Compliance 				X 	X	X	X	X	X	X	X	X	X	X	X
Weighted child intentional communication score	X		X		X		X	X	X		X	X			X
Auditory ERP 	X 		X		X		X		X						X
Mullen Scales of Early Learning	X		X		X				X						X
Vineland Adaptive Behavior Scale-3	X		X		X		X	X	X			X		X	X
Preschool Language Scale - 5	X		X		X				X						X
MacArthur Vocabulary Scale	X		X		X		X	X	X			X		X	X
VAS-Language	X	X	X	X	X	X	X	X	X	X	X	X	X	X	X
CGI-I 		X	X	X	X	X	X	X	X	X	X	X	X	X	X
CGI-S 	X	X	X	X	X	X	X	X	X	X	X	X	X	X	X
VAS-Behavior	X	X	X	X	X	X	X	X	X	X	X	X	X	X	X
ABC-FX	X		X		X		X	X	X		X	X			X
Eye Tracking 	X 		X		X		X		X						X
Children's Sleep Habits Questionnaire	X		X	X	X				X	X	X				X

AFQ056 for Language Learning in Children with FXS  
 Version v15  
 Version date 02/03/2021

1. CBC, Comprehensive Metabolic Profile (CMP), TSH at screening, 2, 8, 10, 16 months.
2. Cellular biomarkers: ERK, AKT, S6 kinase, APP, and MMP9 at screening, 2, 8, 10, 16 months, DNA banking at screening, RNA, protein, serum banking at screening, 2, 8, 10, 16 months.
3. Visit windows are  $\pm$ 5 days for v2-v3 based on the date of Visit 1, and  $\pm$ 5 days for v4-v15 based on date of visit 3.
4. Dose titration done weekly from the baseline visit (v3) to the 2 month visit (v5) and from the 8 month visit (v9) to the 10 month visit (v1). Please refer to the Manual of Operations for more details regarding how the dose titration reviews should be done.
5. Wean over 1-2 weeks for dose >25 mg.
6. The 2 month visit is the language intervention baseline assessment visit and in addition to monitoring of the language intervention at study visits, video-conferencing calls will be done with the language therapist to monitor and for ongoing training with the language intervention weekly for 4 months with a  $\pm$ 2 day window between v5 –v8, then monthly with a  $\pm$ 7 day window for the duration of the trial.
7. As possible (expected >50% of cohort).
8. The PI (a fragile X specialist) will perform the funduscopic examination. Many of the study assessments depend on the child's visual function and constitute functional vision assessments. All clinicians and assessors will be trained to observe for evidence of visual compromise during other routine visits and assessments. If any evidence of visual compromise is noted during any of these assessments, the patient will be sent for an ophthalmology exam for further evaluation.
9. For this study two sets of CGI-S/CGI-I will be used. The Language/Communication CGI-S/CGI-I will be anchored to language development. The Overall Function CGI-I/CGI-S will take into account all areas of function including cognition, adaptive behavior, and maladaptive behavior and will be anchored to the child's overall functioning in the home and environments outside the home relative to a typical child of the same age.
10. SLPs will set up 1-2 distance technology training sessions with the subject family during the first month of the trial (after visit 4 – Month 1). During the call, SLPs will review the technology procedures, work with the parent/primary caregiver to set up the intervention environment and work on setting up the equipment as necessary for the language intervention. These practice calls will need to be completed prior to visit 5 (Month 2), after which the language intervention will begin. Please refer to the SLP Training Manual for more details.
11. The ADOS can be administered at any point between Screening and Baseline (i.e. visits 1, 2 or 3), but must be done prior to randomization.
12. Subjects must be at least 3 years old at the time of randomization.
13. If the PK and biomarker blood samples cannot be collected at the screening visit, sites may collect them at the -2 month or baseline visits (v2 or v3) as long as it is prior to randomization. If the PK and biomarker samples cannot be obtained at a visit following randomization (v5, 9, 11 and 14), then the sample can be re-drawn at the next visit to the site.
14. Urine dipstick testing should be completed during the screening visit when possible. If the urine dipstick testing cannot be completed at the screening visit, sites may collect them at the -2 month or baseline visits (v2 or v3) as long as it is prior to randomization. If the urine dipstick testing cannot be obtained at a visit following randomization (v5, 9, 11 and 14), then the sample can be collected at the next visit to the site. For more details please refer to the Manual of Operations.
15. If the auditory ERP, eye tracking, and/or EKG cannot be administered at the screening visit, sites may administer them at the -2 month visit (v2).
16. For subjects with an open label extension that is less than 6 months, a termination visit will occur prior to drug expiration), the length of the open label extension, and the number of months between Visit 11 and Visit 14, will be determined based on when the subject is consented and their dose in the open label extension. .

AFQ056 for Language Learning in Children with FXS

Version v15

Version date 02/03/2021

For those for whom the open label extension is shortened, all study visits will occur at the usual times in the protocol, but an early termination visit will be conducted by August 31, 2021 and if possible visit 15 occurring approximately 1 month later.

17. If a subject is withdrawn from the study during the placebo-lead in period or prior to randomization, they will be brought back in for an abbreviated follow-up/termination visit. Please refer to Section 4.3. Subject Withdrawal Criteria for more details. Subjects withdrawing early (after randomization has occurred) will complete an end of study visit at which assessments and procedures for the 16 month visit (v14) will be conducted, and then if possible will complete a follow up visit at which the same procedures as listed for the 17 month follow up visit (v15) will be conducted. If subjects discontinue study drug prior to the early termination visit, only safety outcomes are assessed during the termination visit (Blood draw, urine dipstick, EKG, vitals, physical, neurological and psychological exams, suicidality assessment, fundoscopic exam, AE review, study drug accountability) and a follow-up email or phone call to document adverse events will be completed 30 days later.
18. If the safety sample obtained at screening visit cannot be analyzed, the sample can be re-drawn at visit 2. In this case dosing can begin, but the results from the repeat blood test must be obtained and acceptable before randomization can be done at Visit 3. If a lab result is abnormal and deemed not clinically significant by the Site Investigator, dosing may proceed. If the safety samples cannot be obtained at a visit following randomization (v5, 9, 11 and 14), then the sample can be re-drawn at the next visit to the site.
19. Depending upon the timing of the visit, the evening/p.m. dose may be administered after the completion of the visit. If the visit is done earlier in the day, the family will retain the current bottle being used in order to administer the evening dose on the day of visit 3. The bottle diluted at visit 3 will then be used starting with the morning dose the day after the visit. This bottle will be then be returned at visit 4 so that site study staff may complete accountability documentation. Please see the NN107 FX LEARN MOP for details about data entry related to accountability.
20. Visit 4 (Month 1), Visit 6 (Month 3) and Visit 10 (Month 9) can be completed remotely if travel to these visits is difficult for the family. All parent rated measures and questionnaires should be completed over the phone. Vitals are optional for these visits. Flexible assessments missed at a visit just prior to a remote visit can be completed after the remote visit, during the next visit to the site. See footnotes 13, 14, and 18 above.
21. The ADOS can be administered using the alternative instructions found in section 6.3.9 "Autism Diagnostic Observation Scale – 2 (ADOS-2)" if the participant is using personal protective equipment which would prevent full completion of the ADOS.

## 6.2 Timing of Study Activities

Visits are shown in the schedule of activities Table as:

- Screening (visit 1, when the subject will be evaluated to determine if he/she qualifies for the study, assessments will be done and subject will start placebo lead-in)
- -2 months (visit 2) when subject will follow up to track progress
- Baseline (visit 3, when pre-intervention assessments are done and the patient is randomized to AFQ056 or placebo)
- Monthly and Bi-monthly visits after Baseline as well as assigned visit number, in order, from the 1 month (visit 4) to 16 month (visit 14) visits
  - The 2 month visit (visit 5) is the language intervention baseline visit when assessments will be obtained on the optimized dose of AFQ056/placebo, and then the language intervention will be implemented.
- Follow Up (the final visit when the subject returns for a safety check after the AFQ056 has been discontinued at the end of the study).

### Visit windows will be as follows:

- Month -2 (v2) and Baseline (v3)  $\pm 5$  days based on the date of Screening (v1)
- Month 1 (v4) through Month 17 (v15)  $\pm 5$  days based on the date of Baseline (v3)

Visits may be split over two days if necessary to lessen the burden of the assessments on the parent(s)/legal guardian and child. The Screening visit may be split over 2 days within a week apart. If the visit will be split over two days more than a week apart, the site must contact the Study Team prior to proceeding. For all subsequent visits that are split over two days, both days must fall within the protocol-specified visit window. If one day should fall outside the window, please contact the Study Team prior to proceeding.

### 6.2.1 Screening/Pre-Randomization Evaluations/procedures

At the beginning of the Screening visit, informed consent to enable participation in the study will be obtained from a legally authorized representative, a parent or legal guardian, by licensed physician investigator delegated to obtain consent. Screening assessments will be completed after consent, after which the subject will receive bottles for placebo lead-in at the end of the visit. The purpose of the screening period is three-fold: to confirm eligibility before randomization, to stabilize placebo effect, and to allow a control group for the language intervention/placebo group.

If the subject does not meet eligibility criteria he/she will be discontinued before the -2 month visits (visit 2) and neither visit 2 nor the baseline visit will be completed. If eligible, the patient will complete the -2 month visit for dispensing of placebo bottle and adverse event review. The subject will be randomized during the baseline visit but will not receive new study medication until all procedures at the baseline visit have been completed. In case a baseline visit needs to be split between multiple days, baseline visits may begin up to 48 hours before the first dosing day with the medication post-randomization. Typically, the Baseline visit will occur the day before the first day of post-randomization dosing.

If a patient fails to meet an eligibility criterion that the investigator deems may change over time, such that the patient may qualify if screened again at a later date, the patient may be re-screened for eligibility. The re-screening visit must occur at least 4 weeks after the initial screening visit occurred. If a patient is re-screened, all inclusion and exclusion criteria must be reassessed prior to final eligibility determination.

## **6.2.2 On-Study/On-Interventions Evaluations/procedures**

Study visits after Baseline will occur at 1 (visit 4), 2 (visit 5), 3 (visit 6), 4 (visit 7), 6 (visit 8), 8 (visit 9), 9 (visit 10), 10 (visit 11), 12 (visit 12), 14 (visit 13), and 16 (visit 14) months while the subject is taking study medication/placebo. Visit windows for visits 4 through 15 will be  $\pm 5$  days base on the date of Baseline (v3).

Dose titration reviews will be done weekly with a recommended  $\pm 1$  day window to evaluate side effects and adjust study medication dose between Baseline (visit 3) and visit 5 in the placebo-controlled period, and between visit 9 and 11 in the open-label extension. Video conference calls will be done with the language therapist to monitor and for ongoing training with the language intervention weekly for 4 months, then monthly with a  $\pm 7$  day window for the duration of the trial (through the open label portion).

The schedule of activities at each study visit will depend somewhat on subject cooperation and family perception of the best order of activities for the subject in question. In general, if the visit is being conducted on a single day, the play-based assessment and developmental and language testing will be done first, followed by the eye tracking and auditory ERP, as applicable, and formal medical exams. EKG and blood work, will typically be done last. If the visit is conducted over multiple days these events will be re-organized with the general principle of doing activities for which patient performance is important (play-based assessment, developmental and language testing, and ERP/eye tracking) will be given priority as initial assessments on each day, again with parent input as to the preferences and types of activities that will be difficult for the child. The parent completed measures, adverse event review, dosing diary review and dosing/compliance discussion and interim history can be done with the family while the subject is undergoing testing at visits that require subject testing. If the subject cannot complete testing without the parent present in the testing room, the parent will accompany the subject to testing and discussions with the parent will be done when the medical assessments are completed.

## **6.2.3 Study Medication/Intervention Discontinuation Evaluations/procedures**

Study medication/intervention discontinuation will occur when subjects complete the study or withdraw from the study early (after randomization). At study completion, subjects will complete all the assessments and procedures for the 16 month visit (visit 14).

If a subject withdraws from the study after randomization, a Termination visit should be conducted as soon as possible. The assessments and procedures completed during the termination visit will depend upon whether the subject discontinued study drug prior to the termination visit. Assessments and procedures are to be completed as possible based on agreement of the caregiver at the termination visit(s) as follows:

- The subject is on study drug at the time of the visit
  - The termination visit will include all the assessments and procedures for the 16 month visit (visit 14).
- The subject discontinued study drug prior to the visit
  - The termination visit will include the following safety assessments and procedures
    - Blood draw
    - Urine dipstick
    - EKG
    - Vitals
    - Physical, neurological and psychological exams
    - Suicidality assessment
    - Fundoscopic exam

- AE review
- Study drug accountability

A follow up visit after the Termination Visit with the subject off study drug should be conducted 30 days after the termination visit.

Study medication will be weaned over 1-2 weeks for subjects on a dose of >25 mg BID AFQ056 or placebo, and stopped without weaning for subjects on a dose of 12.5 or 25 mg BID. For participants on a dose of 50 mg BID, the dose will be weaned to 25 mg BID for a week and then stopped. For participants on 75 mg BID or 100 mg BID, the dose will be weaned to 50 mg BID for a week and then to 25 mg for a week, and then stopped.

Discontinuation criteria for individual subjects are listed in section 4.3 of the protocol – please refer to that section for more details.

The entire trial will be stopped if 3 serious adverse events considered probably or definitely due to drug occur or upon recommendation by the DSMB based on unblinded review of adverse events.

Dosage reductions will be allowed down to 12.5 mg BID during dose titration periods. If a down titration is needed during the fixed dose period because of side effects, the subject will be withdrawn from the study. If a subject cannot tolerate even the 12.5 mg BID dose, that subject will be withdrawn from the study. Subjects may be withdrawn from the study if there is a temporary suspension of dosing for more than 7 consecutive days or for more than 14 days total.

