## 9.9 Data Monitoring

All aspects of the study will be monitored by qualified individuals designated by the sponsor. Monitoring will be conducted according to Good Clinical Practice and applicable government regulations. The investigator agrees to allow monitors access to the clinical supplies, dispensing and storage areas, and to the clinical files of the study subjects, and, if requested, agrees to assist the monitors.

Safety monitoring will include careful assessment and appropriate reporting of adverse events. Medical monitoring will include contemporaneous assessment of serious adverse events.

The monitoring of subject safety and data quality will follow the NINDS Guidelines for Data and Safety Monitoring in Clinical Trials. A Data and Safety Monitoring Board (DSMB) appointed by the NIH/NINDS will meet at six-month intervals (or as determined by the NINDS) to review partially unblinded study data provided by the study statistician. This committee will monitor rates of adverse events and endpoints in the trial and will monitor the performance of the trial. The frequency and format of DSMB meetings, reports, and guidelines for interim analysis will be agreed upon prior to study subject enrollment.

The Protocol PI will appoint an Independent Medical Monitor (IMM) to review all adverse events, in a blinded fashion, on a periodic basis. In addition, the IMM will review all events that meet the regulatory definition of a Serious Adverse Event, upon receipt of notification via the Electronic Data Capture (EDC) system.

An adverse event (AE) is any unfavorable and unintended sign (including a clinically significant abnormal laboratory finding, for example), symptom, or disease temporally associated with a study, use of a drug product or device whether or not considered related to the drug product or device. FDA, Office of Human Research Protection (OHRP), and NeuroNEXT CIRB requirements for reporting AEs will be followed. Subjects will be monitored for AEs from the time they sign consent until 30 days following permanent discontinuation of study drug. At that point, all ongoing AEs will be followed to resolution, but no new AEs will be recorded. The IMM/DSMB will review cumulative AEs; the frequency of this review will be determined by the IMM/DSMB in conjunction with the Protocol PI.

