### ***On-line Adverse Event Reporting System***

Upon entry of a serious adverse event by a site investigator, the DCC Online Adverse Event Reporting System will immediately notify the Independent Medical Monitor (IMM).

- Within **24 hours** (of learning of the event), investigators must report any Serious Adverse Event (SAE). Investigators should report all other AEs within **5 working days/7 calendar days** (of learning of the event).

Serious adverse events: The site investigator determines causality (definitely not related, probably not related, possibly related, probably related, definitely related) of the adverse event. The IMM will review the SAE report. The IMM may request further information if necessary. The Online Adverse Event Reporting System maintains audit trails and stores data (and data updated) and communication related to any adverse event in the study. The IMM may determine that the Serious Adverse Event requires expedited reporting to the FDA. The DCC will prepare a MedWatch safety report for submission to the FDA. If warranted, the IMM will notify the DSMB chair. The DSMB may suggest changes to the protocol or consent form to the Study Chair as a consequence of adverse events.

Non-serious adverse events: Non-serious adverse events that are reported to or observed by the investigator or a member of his research team will be submitted to the DCC in a timely fashion (within 5 working days). The events will be presented in tabular form and given to the IMM on a quarterly basis or as requested. Local site investigators are also required to fulfill all reporting requirements of their local institutions.

The DCC will prepare aggregate reports of all adverse events (serious/not serious, expected/unexpected and relationship to study drug) for the IMM and the DSMB on a quarterly basis or as requested. In addition, all adverse events will be coded using the MedDRA system. A separate report detailing protocol compliance will also be available from the DCC for DSMB and/or site review monthly or as requested. The research team will then evaluate whether the protocol or informed consent document requires revision based on the reports.

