#### **10.4.1.2 Serious Adverse Events**

A serious adverse event (SAE) is defined as an adverse event that meets any of the following criteria:

1. Results in death.
2. Is life threatening: that is, poses an immediate risk of death as the event occurred.
  - a. This serious criterion applies if the study subject, in the view of the Site Investigator or Sponsor, is at immediate risk of death from the AE as it occurs. It does not apply if an AE hypothetically might have caused death if it were more severe.
3. Requires inpatient hospitalization or prolongation of existing hospitalization.
  - a. Hospitalization for an elective procedure (including elective PEG tube/g-tube/feeding tube placement) or a routinely scheduled treatment is not an SAE by this criterion

because an elective or scheduled “procedure” or a “treatment” is not an untoward medical occurrence.

4. Results in persistent or significant disability or incapacity.
  - a. This serious criterion applies if the “disability” caused by the reported AE results in a substantial disruption of the subject’s ability to carry out normal life functions.
5. Results in congenital anomaly or birth defect in the offspring of the subject (whether the subject is male or female).
6. Necessitates medical or surgical intervention to preclude permanent impairment of a body function or permanent damage to a body structure.
7. Important medical events that may not result in death, are not life-threatening, or do not require hospitalization may also be considered SAEs when, based upon appropriate medical judgment, may jeopardize the subject and may require medical or surgical intervention to prevent one of the outcomes listed in this definition. Examples of such medical events include blood dyscrasias or convulsions that do not result in inpatient hospitalization, or the development of drug dependency or drug abuse.

An inpatient hospital admission in the absence of a precipitating, treatment-emergent, clinical adverse event may meet criteria for "seriousness" but is not an *adverse* experience, and will therefore, not be considered an SAE. An example of this would include a social admission (subject admitted for other reasons than medical, e.g., lives far from the hospital, has no place to sleep).

A serious, suspected adverse drug reaction is an SAE that, in the opinion of the Site Investigator or Sponsor, suggests a reasonable possibility that the investigational product caused the event.

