#### **Relatedness of Adverse Event to Investigational Product**

The relationship of the AE to the investigational product should be specified by the Site Investigator, using the following definitions:

1. Not Related: Concomitant illness, accident or event with no reasonable association with treatment.

2. Unlikely: The reaction has little or no temporal sequence from administration of the investigational product, and/or a more likely alternative etiology exists.
3. Possibly Related: The reaction follows a reasonably temporal sequence from administration of the investigational product and follows a known response pattern to the suspected investigational product; the reaction could have been produced by the investigational product or could have been produced by the subject's clinical state or by other modes of therapy administered to the subject. (suspected ADR)
4. Probably Related: The reaction follows a reasonably temporal sequence from administration of investigational product; is confirmed by discontinuation of the investigational product or by re-challenge; and cannot be reasonably explained by the known characteristics of the subject's clinical state. (suspected ADR)
5. Definitely Related: The reaction follows a reasonable temporal sequence from administration of investigational product; that follows a known or expected response pattern to the investigational product; and that is confirmed by improvement on stopping or reducing the dosage of the investigational product, and reappearance of the reaction on repeated exposure. (suspected ADR)

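### Read literally, the relatedness definitions keep a first-episode fatal SAE out of the three-SAE stopping count; one sentence would settle it

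*Combined protocol and SAP*

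**What the plan says.** Section 6.2.3 gives the whole-trial rule: the entire "trial will be stopped if 3 serious adverse events considered probably or definitely due to drug occur or upon recommendation by the DSMB". The DSMB limb, "or upon recommendation by the DSMB based on unblinded review of adverse events", is a separate route with no causality filter. The sentence cites no definition and does not say whose judgement counts.

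Section 10.4.1.3, under the relatedness subheading, says: "The relationship of the AE to the investigational product should be specified by the Site Investigator, using the following definitions". Three of its five categories matter here.

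- 'Possibly related' has no discontinuation or re-challenge condition.
- 'Probably related' requires, among other things, that the reaction "is confirmed by discontinuation of the investigational product or by re-challenge; and cannot be reasonably explained" by the known features of the child's clinical state.
- 'Definitely related' requires that it be "confirmed by improvement on stopping or reducing the dosage of the investigational product, and reappearance of the reaction on repeated exposure".

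No exception is given for fatal or irreversible events. Section 10.4.1.2 lists "Results in death" as its first SAE criterion.

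The SAE paragraphs in Section 10.4 (On-line Adverse Event Reporting System) and Section 10.4.1.3 (AEDAMS) have the site investigator rate causality on a five-step scale. It shares the top three labels, but no step is defined and no such condition is attached. Sections 5.1 and 6.3.9 also use the labels undefined.

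On oversight, Section 9.9 says the DSMB "will meet at six-month intervals (or as determined by the NINDS) to review partially unblinded study data". Section 10.4 has the Independent Medical Monitor (IMM) notified immediately of each SAE, and adds: "If warranted, the IMM will notify the DSMB chair".

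**The concern.** The three-SAE count is the only numerical rule in the document for stopping the whole trial. A reader would expect a drug-caused death to count toward it before any milder event. If the definitions are applied as written, a child's first and fatal reaction cannot meet either qualifying label, however suggestive the timing and however weak the alternative explanations. The count would then register reversible serious events and miss the gravest one, in a trial of children aged 3 to 6. Stopping after a death would rest on discretionary routes alone.

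**Working it through.** The plan gives no derivation for the threshold of 3 (no assumed SAE rate, error rate or power), so there is no figure to reproduce. The check is logical.

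**Step 1. Apply each category in Section 10.4.1.3 to a fatal SAE with no earlier episode of the same reaction.**

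| Category | Condition that decides | Met? |
|---|---|---|
| Definitely | Improvement on stopping or reducing the dose, and recurrence on re-exposure | No |
| Probably | Confirmation by discontinuation or re-challenge, joined to the other conditions by 'and' | No |
| Possibly | No such condition | Can be met |

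The ceiling is 'possibly', which Section 6.2.3 does not count.

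**Step 2. Is re-challenge otherwise available after an SAE?** Sections 4.3 and 8 call for discontinuation and withdrawal after an SAE suspected to be drug-related. In practice, reaching 'probably' therefore depends on improvement after discontinuation. A death cannot show that.

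**Step 3. Effect on the count (3 needed).**

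- One such death: 0 as written, 1 with the fix.
- Two SAEs that resolved on discontinuation and were rated 'probably', plus one such death: 2 + 0 = 2 as written (no stop on the count); 2 + 1 = 3 with the fix (stop).

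A single death does not reach 3 under either wording. The gap matters only when other counted SAEs have already occurred.

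**Step 4. Set the two texts side by side.** The relatedness definitions are the only ones given, and the site investigator is directed to use them. The SAE reporting paragraphs are specific to SAEs and use the same upper labels, but add no condition. An investigator following the first rates the death 'possibly'. One following the second may rate it 'probably'. The count is then 0 or 1 for the same event.

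**Step 5. How often could the count be in play?** Section 2.2 reports no SAE in about 300 FXS patients exposed to AFQ056.

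- One-sided 95% upper bound on the SAE rate: 1 − 0.05^(1/300) = 0.0099, or 0.99%.
- Children exposed here: 50 on active drug plus up to 50 placebo children entering the extension = up to 100.
- Expected SAEs at the bound: 100 × 0.0099 = 0.99.
- Poisson chance of 3 or more at that mean: 0.079, or 7.9%, treating every SAE as drug-related and counted.

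This is a ceiling on how often three SAEs would occur at all under that history, not an estimate of how often the gap would matter. At the observed rate of zero the figure is 0.

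**The case against.** Four points have weight.

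1. **The cap is not absolute.** A reader might infer that no drug-caused death could ever count. The documents do not support that. The definitions ask whether the reaction was confirmed, not whether the outcome reversed. Section 6.3.14 allows a dose to be reduced and then re-escalated during titration. Section 3 describes an acute drop to 25 mg BID and re-titration at month 8 for children who had been on 50 to 100 mg BID of active drug. A reaction that eased and returned in this way before a fatal recurrence could arguably qualify. The point is therefore limited to a fatal SAE without such a history.

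2. **The link between the sections is inferred.** Section 6.2.3 does not cite Section 10.4.1.3. The link rests on matching labels and on there being no other definitions. This stands, and it makes the defect partly one of ambiguity. A trial-stopping rule should not turn on which section is consulted.

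3. **Oversight is substantial.** A reader might infer that a death would go unreviewed or that the trial could not be stopped. That is not so. The DSMB limb is in the same sentence as the count. SAEs are reported within 24 hours, and the monitor is notified at once and reviews each report. Aggregate reports go to the DSMB quarterly or on request. A 'possibly related' event is still a suspected adverse drug reaction, and if unexpected it falls under expedited reporting. Section 11.3 lets the CIRB, NINDS, sponsor, OHRP, FDA or other government agencies stop the study. Section 9.9 leaves DSMB reports and meeting format to a separate agreement that is not in the document, so nothing can be said about how the DSMB would handle a death. These routes cover most of the practical risk, but they are discretionary and do not make the count itself correct.

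4. **Permanent injury is less clear than death.** The text does not explain what confirmation by discontinuation would mean for an injury that persists. The death case does not depend on this.

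**Conclusion.** The point holds in a limited form. Under the only definitions given, a fatal SAE with no earlier discontinuation or re-challenge episode of the same reaction rates 'possibly' at most and adds 0 to the count. Under the SAE reporting text it might be rated 'probably' and add 1. The conclusion assumes that the labels in Section 6.2.3 carry the meanings in Section 10.4.1.3 and that investigators apply them literally.

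The practical effect is small: likelihood is low, and the other routes to stopping do not depend on the rating.

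A reader might want to turn Step 5 into a probability that the omission decides the outcome. If 5% to 25% of SAEs went uncounted, the chance of reaching 3 at the upper bound would fall by 0.9 to 3.9 percentage points. The documents do not support using that as an estimate. They give no fatal share; the assumed share pools deaths with permanent injuries. The calculation also stacks a 95% upper bound on the assumption that every SAE is drug-related and otherwise counted. Nor do the 300 patients match this population. Most were adults or adolescents, with exposure from single doses to over 2 years. The paediatric study treated 21 children, with about a week of repeated dosing. No reliable probability can be given in either direction.

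The case for changing the text is that a safety rule should give the right answer for its gravest event, and that the correction is nearly free.

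**What to change.** Add one sentence to the relatedness definitions in Section 10.4.1.3, or to the stopping rule in Section 6.2.3: for a fatal SAE, the discontinuation or re-challenge condition is waived, so that an event with a reasonable temporal sequence and no reasonable alternative explanation may be rated 'probably related' and counts toward the 3. Extend the waiver to a permanent injury only where improvement off drug is impossible. Leave the threshold of 3 and the rating of all other events as they are.

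The cost is one sentence. The downside is that slightly more events may count toward stopping.
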